## 1. PROTOCOL BACKGROUND

### 1.1 Describe the scientific/scholarly rationale and background for your project. Describe the gaps in current knowledge your project is intended to address.

**Importance of the problem.** There were nearly 100,000 overdose deaths in 2020, with 75% of the 93,331 related to opioids. Many Americans suffer because of the loss of a family member to opioid use disorder (OUD), and the direct and indirect costs of substance use disorders (SUDs) to society are estimated to be over \$600 billion annually. Because only 17% of people with OUD get medication assisted treatment (MAT) each year, the majority remain at heightened risk for overdose, death, and other harmful personal and societal outcomes. Community Reinforcement and Family Training (CRAFT) significantly improves treatment entry and retention of treatment-resistant individuals. It is delivered by counselors to a family member or concerned significant other (CSO) motivated to help their loved one with an OUD (Identified Persons, or IPs). It has strong empirical support, having been tested by multiple investigators in 10 well-controlled clinical trials, with consistently moderate to large effects on treatment entry (62-77%) vs treatment controls (17-40%). In addition, two OUD-focused studies found that CRAFT improved retention in MAT such that IPs were less likely to drop out of treatment compared to usual practices. Unfortunately, CRAFT is broadly inaccessible to families because most counselors do not receive CRAFT training.

Approximately \$70 million is spent annually to train SUD treatment providers and billions of dollars are spent to develop and validate the efficacy of Empirically Supported Treatments (ESTs) like CRAFT, but these treatments are rarely used in treatment programs. Moreover, when they are used, the quality of their implementation is usually poor. It is

critical that we find effective ways to train counselors to implement CRAFT if we are to address the toll that OUDs are taking on individuals, their families, and the American public.

**Critical barrier to progress.** Currently, CRAFT counselor training lacks scalability. Training workshops are held in-person or through web-conferencing by [name], the developer of CRAFT, or by a few trainers approved by him. [name] has a post-workshop certification process that is user-friendly and allows counselors to securely upload digital audiotapes to a server where they are manually coded by trained raters who generate written feedback on CRAFT adherence and skill. During web-based coaching sessions, additional feedback and advice is provided. This process trains counselors to proficiency in CRAFT and then certifies them; however, it is expensive, has limited scale, is largely dependent on one person ([name]), and has not been leveraged to take full advantage of a digital format. No comprehensive digital CRAFT training and certification programs for counselors exist.

**Research.** Current methods for training counselors and disseminating ESTs, including CRAFT, rely on brief online or in-person workshops. However, research shows this format is minimally effective in facilitating adoption and implementation of ESTs. Counselors who receive post-workshop feedback and coaching on taped sessions with clients show larger gains in proficiency and maintain them longer. Much of this well-controlled research has examined in-person counselor training for motivational interviewing and cognitive behavior therapies. Because CRAFT uses a motivational interviewing approach and is based in cognitive behavior therapy, it is very likely that the effectiveness of these procedures generalizes to CRAFT training; however, no studies have specifically examined CRAFT counselor training and very few controlled studies have evaluated scalable online training.

Most internet training studies have had small sample sizes, no control group, and/or relied on knowledge-based and self-report measures that do not necessarily reflect actual change in counselor behavior. Of the three studies that used the preferred method of direct observation of counselor proficiency, two had no control comparison but found pre to post training improvements after an online tutorial followed by live remote observation with feedback and coaching. The third study found improvements in Motivational Interviewing proficiency for counselors receiving feedback on taped sessions or live supervision of sessions at 8 and 20 weeks post-workshop and these improvements were greater than for a workshop alone group. We found no randomized controlled trials of counselor web-based training that examined CRAFT.

**Contributions.** The development and rigorous testing of a scalable CRAFT counselor training product will contribute to scientific knowledge because:

1. Replication and generalization of the previous counselor training research is needed. Research on web-based counselor training is limited, and no studies have examined training in CRAFT.
2. Most studies have not examined the feasibility and necessity of training counselors to proficiency. This project will be the first to explore the effect of different levels of training on family outcomes.
3. Web-based training programs have not fully explored the potential of the digital format to leverage automation in training staff efficiently. It is possible that fully digitized self-study materials could allow some counselors to significantly improve their proficiency or even prepare to achieve certification.
4. Additional studies would better establish methods for maintaining EST skills. Few web-based training trials have examined skills maintenance past the end of the most intensive training group.

## 1.2 List the primary and secondary aims, research questions, and hypotheses.

**The goal of this project is to develop and evaluate the technical feasibility and commercial viability of a scalable digital counselor training program for CRAFT.** This Phase I project will develop an enhanced training model for CRAFT and digitize it to maximize scalability. In this project, we will:

**Aim 1:** Produce the digital counselor training prototype and coaching process, tailored to OUD - with stakeholder input.

**Aim 2:** Conduct a pilot study of 3 levels of digital training (Level 1 – Digital tutorial only [T]; Level 2 – Tutorial & digital training materials for self-study [TM]; Level 3 – Tutorial, digital materials, feedback and coaching [TMC]) to

establish feasibility, acceptability, and examine the effects of training on CRAFT knowledge, fidelity, and treatment entry and retention.

1. Primary Hypothesis
  - 1.1. At 12 weeks (after study start), participants assigned to the TMC condition will demonstrate the highest CRAFT procedure fidelity (measured in audiotaped sessions with a standardized patient) followed by TM and then T.

*Rationale:* Direct observation measuring content of CRAFT delivered in treatment sessions is our primary outcome as this provides the best assessment of counselor adherence and skill and is consistent with previous studies. Our hypothesis that TMC will produce greater use of CRAFT than T (or TM) is based on the results from previous trials comparing a workshop only to workshops plus feedback and coaching.
2. Secondary Hypotheses
  - 2.1. Participants assigned to the TMC condition will demonstrate the highest CRAFT knowledge followed by TM and then T, in their 12-week knowledge test.

*Rationale:* Results from previous controlled trials have shown no differences in counselor knowledge pre- to post-workshop, but increases have been seen when fact sheets and supervision are added after the workshop.
  - 2.2. Participants will rate the programs satisfactory, useful and usable with similarly positive scores (3 on a 5 point scale or above) at each follow-up assessment point.

*Rationale:* Research shows (and with our own CRAFT Family product) that all programs are rated similarly satisfactory and useful.
  - 2.3. Participants in all conditions will perceive increased implementation potential over time (pre-tutorial, post-tutorial, 12 week follow up), but at 12 weeks implementation potential will be lower for TMC compared to TM and T.

*Rationale:* In a CBT (Cognitive Behavioral Therapy) web-based training study implementation potential of three training programs increased over time, but a condition involving expert supervision was seen as more difficult to implement.
  - 2.4. Participants assigned to the TMC condition will assign the highest monetary value to the tutorial, digital training and certification components, followed by TM and then T participants, in their 12-week follow-up surveys.

*Rationale:* The pilot study of our CRAFT Family product showed participants assigned to the CRAFT private coaching condition valued all components of the program substantially higher than those who received less coaching in the group condition, or digital only (no coaching) condition.
  - 2.5. Participants assigned to the TMC condition will report that more IPs have entered treatment compared to TM and T at 12-weeks (after study start) follow-up surveys.

*Rationale:* This hypothesis is based on the results from previous trials examining counselor fidelity and studies showing that CBT fidelity enhances treatment outcome. *We consider this hypothesis exploratory because the 6 month timeline will not be sufficient to adequately test for differences in treatment entry, as there would not be much time after all counselors completed training for them to complete CRAFT with CSOs.*

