### 1.3 List the primary and secondary outcomes.

The primary outcome variable is the participant's demonstration of procedure fidelity, measured in audiotaped sessions with a standardized patient.

Secondary outcome variables include participant's CRAFT knowledge; participant's satisfaction with the program (website content and delivery); participant's perceived implementation potential; participant's monetary valuation of the program; and participant's report of IPs entering treatment via CSO report.

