Cover Page: Statistical Analysis Plan
We The Village Counselor Training Study
NCT05875142
Document Date: 09.26.23

Statistical Analysis Plan

Our statistical analysis focuses on a primary endpoint as well as a number of secondary endpoints of interest. The data derive from questionnaires collected from participants in the study. The final enrollment involved three groups: T – Digital Tutorial Overview, TM – Digital Tutorial Plus Training Materials, and TMC – Digital Tutorial Plus Training Materials Plus Feedback and Coaching, with 15, 16, and 16 subjects enrolled, respectively.

1. **T – Digital Tutorial Overview:** Participants assigned to T were given access to a digital tutorial consisting of a curriculum dashboard for review of 10 modules, including videos, PDFs, text and quizzes, which are to be self-administered over two weeks. Modules remain available during the 10-week post tutorial period. Participants receive weekly contact encouraging engagement in all of the materials available to them.
2. **TM – Digital Tutorial Plus Training Materials:** Participants receive the digital tutorial (T) as described above plus access to 10 modules of digital training materials released weekly over the 10-week post tutorial period for self-study. Participants receive weekly contact encouraging engagement in all of the materials available to them.
3. **TMC – Digital Tutorial Plus Training Materials Plus Feedback and Coaching:** Participants receive the digital tutorial (T) plus the digital Training materials as described in the two arms above plus they submit audio recordings of sessions with clients and receive feedback on their application of CRAFT and coaching on how to improve. Participants receive weekly contact encouraging engagement in all of the materials available to them.

Our comparisons are all treatment/control comparisons of T with TM, and T with TMC.

1. Primary Hypothesis
 - 1.1. At 12 weeks (after study start), participants assigned to the TMC condition will demonstrate the highest CRAFT procedure fidelity (measured in audiotaped sessions with a standardized patient) followed by TM and then T.

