Rationale: Direct observation measuring content of CRAFT delivered in treatment sessions is our primary outcome as this provides the best assessment of counselor adherence and skill and is consistent with previous studies.^{7,10,41} Our hypothesis that TMC will produce greater use of CRAFT than T (or TM) is based on the results from previous trials comparing a workshop only to workshops plus feedback and coaching.^{7,10,41}
2. Secondary Hypotheses
 - 2.1. Participants assigned to the TMC condition will demonstrate the highest CRAFT knowledge followed by TM and then T, in their 12-week knowledge test.
Rationale: Results from previous controlled trials have shown no differences in counselor knowledge pre- to post-workshop, but increases have been seen when fact sheets and supervision are added after the workshop.^{39,57-58}
 - 2.2. Participants in all conditions will perceive increased implementation potential over time (pre-tutorial, post-tutorial, 12 week follow up), but at 12 weeks implementation potential will be lower for TMC compared to TM and T.
Rationale: In a CBT (Cognitive Behavioral Therapy) web-based training study implementation potential of three training programs increased over time, but a condition involving expert supervision was seen as more difficult to implement.³⁹

2.3. Participants assigned to the TMC condition will report that more IPs have entered treatment compared to TM and T at 12-weeks (after study start) follow-up surveys. *Rationale:* This hypothesis is based on the results from previous trials examining counselor fidelity^{7,10,41} and studies showing that CBT fidelity enhances treatment outcome.⁵⁹⁻⁶⁰ *We consider this hypothesis exploratory because the 6 month timeline will not be sufficient to adequately test for differences in treatment entry, as there would not be much time after all counselors completed training for them to complete CRAFT with CSOs.*

Data Analysis

Primary and secondary hypotheses were investigated by computing the improvement from baseline to 12-week timepoints. One-sided independent samples T-tests were used for pairwise comparisons of the three conditions. One-sided tests are appropriate for our hypothesized conditions: the alternative hypotheses for which we seek evidence is TMC is better than T, TM is better than T, and TMC is better than TM.

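### Hypothesis 2.2 predicts that the three programs will be rated similarly, but its only criterion is a floor of 3 out of 5, which can show that each program is rated positively and not that the ratings are alike

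*Protocol*

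**What the plan says.** Protocol section 1.2, Hypothesis 2.2, reads: "Participants will rate the programs satisfactory, useful and usable with similarly positive scores (3 on a 5 point scale or above) at each follow-up assessment". The rationale beneath it appeals to research, and to the sponsor's own family product, showing that "all programs are rated similarly satisfactory and useful". Section 1.3 lists "participant's satisfaction with the program (website content and delivery") among the secondary outcomes.

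Table 3 of the protocol schedules the satisfaction, usefulness and usability surveys post-tutorial and at 12 weeks. It gives fidelity and knowledge an explicit ordering of the arms, but marks the acceptability surveys only with a hypothesis number.

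The SAP's list of hypotheses covers fidelity, knowledge, implementation potential and treatment entry. Its own number 2.2 is implementation potential, so the acceptability hypothesis does not appear. Its Data Analysis section works with improvement from baseline to 12 weeks and gives one method: "One-sided independent samples T-tests were used for pairwise comparisons of the three conditions", with alternatives stated as one arm being better than another. The SAP reports the arms T, TM and TMC "with 15, 16, and 16 subjects enrolled, respectively".

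**The concern.** Hypothesis 2.2 contains two claims. One is that each program is rated positively. The other is that the programs are rated alike, and the rationale shows that this is meant as a comparison between programs. The number 3 bears only on the former: it is applied to ratings taken separately, and the difference between arms is never an input. Moving the floor up or down would not change that. Neither document gives a margin, an interval or a test for the latter.

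Acceptability is one of the purposes of Aim 2, and the arms differ in what they would cost to deliver; section 1.1 describes the existing coached certification process as expensive and limited in scale. If all three arms clear 3, a report could say that the levels were rated similarly when the data had shown only that none was rated poorly.

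**Working it through.** The documents give no SD, power or margin for these ratings, so there is no stated figure to reproduce.

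**Inputs.** From the documents: a 5-point scale, a floor of 3, and arm sizes 15 (T), 16 (TM) and 16 (TMC). Assumed: within-arm SD of 0.6, 0.8 or 1.0, approximately normal ratings, every counselor assessed, and the floor applied to arm means (the protocol does not say whether it applies to means or to individual scores).

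**1. How far apart can arms be that all clear the floor?** The scale ends at 5, so two means of at least 3 can differ by up to 5 − 3 = 2 points.

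**2. How often is the floor met with a 1-point gap between T and TMC?** For one arm, P(observed mean ≥ 3) = Φ((μ − 3)/(SD/√n)); the three arms are multiplied. With true means 3.5/4.0/4.5 the lowest arm governs. For T at SD 1.0: (3.5 − 3)/(1.0/√15) = 1.936, and Φ(1.936) = 0.974. The other two arms are practically certain to pass. The same 1-point gap placed lower on the scale gives a different answer:

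| True means T/TM/TMC | SD 0.6 | SD 0.8 | SD 1.0 |
|---|---|---|---|
| 3.5/4.0/4.5 | 99.9% | 99.2% | 97.4% |
| 3.2/3.7/4.2 | 90% | 83% | 78% |
| 3.0/3.5/4.0 | 50% | 50% | 49% |
| 2.8/3.3/3.8 | 10% | 16% | 19% |

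The criterion responds to where the lowest arm sits, not to the gap, which is 1 point in every row.

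**3. Could the trial see that gap?** Standard error of T − TMC = SD × √(1/15 + 1/16) = SD × 0.359. The noncentrality parameter for 1 point is 1/(0.359 × SD) = 4.64, 3.48 and 2.78 for the three SDs. With 29 degrees of freedom and a two-sided 5% test, power is 99%, 92% and 77%. In the first row of the table, then, the floor would nearly always be met while the trial's own data would usually show that the arms differ.

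**4. Could the SAP's test supply the missing comparison?** It looks for superiority, and a non-significant result is not evidence of similarity. For a 0.5-SD difference (15 v 16), power is 27% two-sided and 39% one-sided at 5%, so it would be missed 73% or 61% of the time. The analysis variable does not fit either: Table 3 has no pre-tutorial measurement of usefulness or usability, so improvement from baseline cannot be computed for them.

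**5. Could similarity be shown with a margin?** Half-width of a pairwise interval (15 v 16) = t × SD × 0.359. At 95% (t = 2.045) this is 0.44, 0.59 and 0.74 points; at 90% (t = 1.699) it is 0.37, 0.49 and 0.61 points. By simulation with identical arms, the chance that all three pairwise 90% intervals lie inside the margin is:

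| Margin (points) | SD 0.6 | SD 0.8 | SD 1.0 |
|---|---|---|---|
| ±0.5 | 20% | 1% | 0% |
| ±0.75 | 82% | 37% | 9% |
| ±1.0 | 99% | 82% | 48% |

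The answer depends on the margin, which the documents do not give.

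**The case against.** The best defence is that Hypothesis 2.2 is a prediction, not a decision rule, and that the parenthesis merely defines what counts as positive. Table 3 fits that reading, since it attaches no ordering of arms to the acceptability surveys, and Aim 2 speaks of establishing acceptability, not of comparing it. This stands to a degree: nothing in either document formally declares the arms similar. It does not dispose of the point, because the rationale compares programs, and the word *similarly* then has no criterion behind it. On the lenient reading the word is surplus and can go.

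Four stronger readings are tempting, and the documents do not support them.

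- That the criterion would be met almost whatever the true difference. It would not: with the lowest arm at 3.0 it is met about half the time, and at 2.8 only 10% to 19% of the time.
- That the plan would take a non-significant t-test as proof of similarity. The SAP does not list this hypothesis, so that route is hypothetical. A gap as large as 1 point would also usually be detected.
- That similarity is out of reach at this sample size. That holds for ±0.5 but not for every margin.
- That a choice between training levels hangs on these ratings. No text in either document makes that link, and fidelity is the primary outcome.

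**Conclusion.** The point holds, and it is minor. The floor of 3 can support the statement that each program is rated positively. It cannot support the statement that the programs are rated similarly, and nothing in the SAP fills the gap. In the illustrative case of means 3.5/4.0/4.5, the floor is met 97% to 99.9% of the time despite a 1-point gap that the trial would detect with 77% to 99% power.

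Those percentages rest on the assumed SD range, the chosen means, full follow-up and application of the floor to arm means. The logical point, that arms clearing the floor may differ by up to 2 points, needs only the 5-point scale and application to means; if the floor applies to individual scores, the between-arm difference is still left out. The severity is low because this is a secondary acceptability hypothesis in a pilot.

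**What to change.** In protocol Hypothesis 2.2, delete the word *similarly*, say whether the floor applies to arm means or to individual scores, and judge positivity arm by arm against 3.

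In the SAP, add a short paragraph for satisfaction, usefulness and usability:

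- Report each arm's mean and the three between-arm differences at week 12 with 95% confidence intervals.
- Show the week-2 differences only descriptively. By then all arms have had only the tutorial, so closeness at week 2 is largely built into the design.
- State that neither clearing the same floor nor a non-significant difference is evidence of similarity.

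No equivalence rule is needed. If the sponsor wishes to keep a similarity claim, it must rest on a justified margin fixed before the ratings are seen, and the sponsor should check what 15 to 16 per arm can deliver at that margin. The SAP already reports final enrollment and describes its analysis in the past tense, so it may be too late to fix one; the deletion and the intervals work either way.

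The cost is one word in the protocol, a clarification of the floor and a few lines in the SAP, with no new data, visits or counselors. The sponsor may lose a favourable statement that the programs were rated similarly.

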### 1.3 List the primary and secondary outcomes.

The primary outcome variable is the participant's demonstration of procedure fidelity, measured in audiotaped sessions with a standardized patient.

Secondary outcome variables include participant's CRAFT knowledge; participant's satisfaction with the program (website content and delivery); participant's perceived implementation potential; participant's monetary valuation of the program; and participant's report of IPs entering treatment via CSO report.

## 2. PARTICIPANTS

### 2.1 Describe the general characteristics of the intended primary participant populations, including age range, gender, sexual orientation, racial/ethnic background, socioeconomic status, health status, criminal history, and any other characteristics relevant to the study.

#### **Aim 1 - Qualitative Review:**

We will sample individuals from 4 groups (n=3/group) with a group of: 1) subject matter advisory board (SMAB) members representing customer perspectives (state-level counselor training decision-makers, payors, SUD program administrators), 2) CRAFT trainers and expert supervisors, expanding beyond our immediate network; 3) counselors, and 4) addiction program leaders (Addiction Administrators). Participants will include individuals identified as subject matter experts in the addiction industry and represent different customer audiences. Participants must be older than 19 years (given the profile of addiction professionals we expect no participants will be excluded on this basis).

**Gender Representation:** We anticipate that about 66% of our research participants will be women. We will monitor gender balance of the counselors at the participating clinics and make extra effort to recruit men (e.g., directly conducting outreach to them through addiction treatment providers and emphasizing the benefits of participation) if they appear to be appreciably under-represented.

**Racial/Ethnic Representation:** Given the Phase I timeline and the early stage and budget we do not anticipate conducting extensive explicit efforts.

**Socioeconomic status:** Because we will be sampling from counselors, counselor training decision makers, payers and administrators we would expect a wide range of income - from around \$30,000 to \$200,000.

